### **3.2.4 Titration Guidelines and Rescue Therapy**

Initiation and titration of tolvaptan must occur in a hospital setting. Up titration can only take place on Treatment Day 2 (or 2a). Titration (up or down) may not occur within 20 hours of the previous dose. Up-titration is limited to no more than twice the previous dose.

The medical monitor should be contacted at any point if questions arise regarding titration or initiation of rescue therapy. The rationale for any up- or down-titration of tolvaptan must be documented. The evaluation of serum sodium levels, management of tolvaptan titration, and rescue therapy is described in [Figure 3.2.4-1](#).

Figure 3.2.4-1 Titration and Rescue Therapy Scheme

1 mEq/L = 1 mmol/L.

**Figure 3.2.4-1 Titration and Rescue Therapy Scheme**

### 3.2.4.1 Titration

Tolvaptan dose titration (after the initial dose) should be based on changes in serum sodium levels as follows:

- If the serum sodium level increases by  $\leq 4$  mEq/L (mmol/L)/24 hours and the subject is still below the therapeutic target for serum sodium level

(135 mEq/L [mmol/L]), then the tolvaptan dose may be titrated up to the next scheduled dose appropriate for the subject's body weight.

- If the serum sodium level increases  $> 4$  to  $\leq 8$  mEq/L (mmol/L)/24 hours in response to tolvaptan treatment and the serum sodium is  $\leq 140$  mEq/L (mmol/L), then the dose of tolvaptan should remain the same for the subsequent day.
- If the serum sodium level increases  $> 8$  mEq/L (mmol/L)/24 hours or reaches a concentration of  $> 140$  mEq/L (mmol/L), then the next dose of tolvaptan should not be given and the medical monitor should be contacted to consider options (ie, down-titration, tolvaptan interruption, concomitant medication adjustment, fluid supplementation and/or withdrawal).
- If serum sodium level increases by [REDACTED] following dosing, or, at any time after dosing, the serum sodium level is  $> 145$  mEq/L (mmol/L), the next dose of tolvaptan should not be given and the medical monitor should be contacted immediately to consider options.

### **3.2.4.2      Rescue Therapy**

Rescue therapy is defined as any treatment, eg, hypertonic saline, isotonic saline (with or without diuretic for purpose of increasing the serum sodium level), plasmapheresis/dialysis, demeclocycline, urea, lithium, or commercially available vaptans intended to raise the level of serum sodium during the trial. Subjects who develop worsening hyponatremia symptoms may receive rescue therapy at any time during the trial.

If at any point during the trial serum sodium levels or hyponatremia symptoms worsen or fail to improve adequately and definitive therapy (eg, isotonic or hypertonic saline) is required, the subject will be withdrawn from trial treatment to receive rescue therapy. Please see Section 4.2 for further details. These subjects will continue to Follow-up Phase C for collection of safety information.

Additional guidelines for rescue therapy concerning hyponatremia symptoms and decreasing serum sodium level:

- If a subject has worsening symptoms and/or has a serum sodium level at or below the baseline value, repeat serum sodium [STAT] to confirm level, and begin rescue therapy.
- If a subject is asymptomatic and serum sodium has decreased by  $\geq 4$  mEq/L (mmol/L), but is still above the baseline value, consider need for rescue therapy according to local standard of care.
- If a subject is asymptomatic and serum sodium has decreased by  $\leq 3$  mEq/L (mmol/L), but is still above the baseline value, no action is required.

Subjects who are randomized to the Early Withdrawal group will initially be observed to determine whether additional intervention is required to maintain appropriate serum sodium levels. For those subjects whose serum sodium declines by  $\geq 4$  mEq/L (mmol/L) or whose overall clinical condition requires further treatment to increase serum sodium, the investigator may consider rescue therapy per local standard of care. Any intervention intended to raise serum sodium level during the first 48 hours in the responder Early Withdrawal group (including fluid restriction) will be defined as rescue therapy. These subjects will be considered to have reached their clinical endpoint, and their data will be censored from that time forward.

Subjects randomized to the Late Withdrawal group who receive rescue therapy will be considered treatment failures. A subject requiring rescue therapy at any time after starting tolvaptan will be discontinued from trial treatment and will proceed to Follow-up Phase C.

### **3.2.4.3 Fluid Restriction Considerations**

In subjects with chronic hyponatremia, fluid restriction coadministered with initiation of treatment with a vaptan has the potential to accentuate the rate of sodium correction and to cause overly rapid correction or over correction of hyponatremia. Therefore, during treatment, subjects must have access to water and maintain fluid intake levels per institutional guidelines. Fluid restriction at any time during the trial including during the first 48 hours after discontinuation of tolvaptan will be considered rescue therapy.

## **3.3 Trial Population**

This trial will include approximately 100 male and female subjects aged  $\geq 4$  weeks (or  $\geq 44$  weeks adjusted gestational age) to  $< 18$  years who have been diagnosed with euvolemic or hypervolemic hyponatremia ( $< 130$  mEq/L [mmol/L]) that persists despite initial standard background therapy (including fluid restriction and excluding a vasopressin antagonist). Age groups will be enrolled such that at least 50% of these subjects will be  $< 10$  years old and at least 25% of subjects  $< 6$  years old. Subjects who are defined as responders will be further stratified by the magnitude of serum sodium response to tolvaptan ( $\leq 7$  and  $> 7$  mEq/L [mmol/L]), age, and underlying etiology of hyponatremia.

### Hyponatremia Etiology in Children and Adolescents

Children with Factor V Leiden or Factor VII abnormalities may be eligible for treatment only if the benefit is judged to outweigh any risk. Tolvaptan may be administered to children with hepatocellular disease (including cirrhosis) who have platelet counts

between 50,000 and 100,000/ $\mu$ L if the need to treat is felt to outweigh the increased risk of GI bleeding.

Children can develop symptomatic hyponatremia more frequently than adults and at less severe levels of hyponatremia because of the large brain volumes in relatively small skulls. The most serious consequence of hyponatremia is hyponatremic encephalopathy, which occurs in over 50% of children with serum sodium < 125 mmol/L.

Hyponatremic encephalopathy is seen in hospitalized children and adolescents in association with SIADH or in the postoperative period. Hyponatremic encephalopathy is a medical emergency that requires immediate intervention; thus, subjects with known risk factors for developing hyponatremic encephalopathy may be ineligible for tolvaptan treatment (eg, hypoxia, infection, brain injury, neurosurgery, uncontrolled seizure disorders, cerebritis, encephalopathy, central nervous system disorders such as cytotoxic and vasogenic cerebral edema, unstable space-occupying brain lesion, or elevated AVP levels).

Symptoms include headache, nausea and vomiting, weakness, confusion, altered consciousness, and lethargy and may progress to more advanced symptoms, including seizures, coma, and death, if untreated. Subjects with overt symptoms of hyponatremia that require immediate intervention to raise serum sodium acutely will be ineligible for tolvaptan treatment; this syndrome is rapidly reversible with hypertonic saline administration.

Additionally, those subjects who are at risk of developing cerebral demyelination will be ineligible for tolvaptan treatment, including subjects who have severe hyponatremia  $\leq$  120 mEq/L (mmol/L), hypernatremia, hypoxemia, severe liver disease, alcoholism, severe burns, severe malnutrition, hypokalemia, diabetes, or renal failure.

Subjects eligible for treatment with tolvaptan will be identified based on serum sodium concentrations that persist at levels  $<$  130 mEq/L (mmol/L). Upon determination of eligibility, each subject's serum sodium will be reassessed just before tolvaptan administration to confirm it remains below this threshold prior to intended treatment initiation.

If any serum sodium value obtained during the pretreatment baseline period for tolvaptan treatment is  $\geq$  130 mEq/L (mmol/L), the subject will be ineligible for tolvaptan administration at that time.

Sorbitol is metabolized to fructose. Subjects who have hereditary fructose intolerance (HFI) who continue to ingest fructose containing products can develop hepatic and renal

dysfunction. The tolvaptan suspension formulation contains sorbitol. Therefore, children who have HFI should not take the tolvaptan suspension formulation.

Hereditary fructose intolerance is typically diagnosed in young children upon the introduction of solid foods containing fructose, sucrose and/or sorbitol (eg, fruits and vegetables). It is not commonly diagnosed in children who are fed exclusively on breast milk. Clinical symptoms can include vomiting, nausea, restlessness, pallor, sweating, lethargy, coagulation disturbances and in some cases, apathy, coma, and convulsions. Laboratory abnormalities may include signs of acute liver failure (eg, elevated serum transaminases, hyperbilirubinemia, abnormal blood clotting factors) or renal failure (eg, proteinuria, generalized hyperaminoaciduria, metabolic acidosis). Continued exposure to fructose can result in hypoglycemia, hepatomegaly, jaundice, steatosis, coagulation disturbances, edema, ascites and signs of proximal renal tubular dysfunction. If HFI is suspected, a thorough history that emphasizes nutritional complaints including the timing of the introduction of fruits and vegetables to the diet should be obtained as well as the appropriate laboratory assessment for confirmation of diagnosis.

For children aged > 2 years, a detailed history with regard to HFI symptoms has to be taken prior to trial entry.

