#### **Pharmacokinetic Sampling**

Blood samples for PK analysis will be obtained at 2 and 8 hours post-first dose, and at trough (24 [ $\pm 4$ ] hours post-previous

dose) on Days 1, 2, 3, and 4 for all subjects dosed with tolvaptan on Days 1, 2, 3, and 4, respectively, regardless of responder status. Pharmacokinetic profiles will be evaluated on an ongoing basis to determine variability among subjects. Based on the findings, PK sampling will continue for as long as necessary to establish suitable estimates of clearance with a 90% confidence interval (CI), similar to that observed in adult subject populations. Once these estimates are achieved, sampling will be discontinued in subsequent subjects in order to minimize blood draws in this pediatric population.
	
Subject Population:	
This trial will enroll approximately 100 male and female subjects to get approximately 70 randomized subjects aged <math>\geq</math> 4 weeks (or <math>\geq</math> 44 weeks adjusted gestational age) to < 18 years who have been diagnosed with euvolemic or hypervolemic hyponatremia (<math>< 130</math> mEq/L [mmol/L]) that persists despite initial standard background therapy (including fluid restriction and excluding a vasopressin antagonist). Age groups will be enrolled such that at least 50% of these subjects will be < 10 years old and at least 25% of subjects < 6 years old.
 
Subjects with acute hyponatremia or hyponatremia expected to resolve spontaneously will be excluded from the trial. Children with an impaired ability to sense or communicate their thirst will either be required per protocol to undergo closer in-hospital observation, laboratory and urine output monitoring, or will be excluded from the trial if this is not possible.
 
The protocol entry criteria have been designed to ensure careful selection of subjects with chronic (<math>\geq</math> 48 hours) dilutional hyponatremia (euvolemic or hypervolemic) associated with heart failure, hepatocellular disease (including cirrhosis), or syndrome of inappropriate secretion of antidiuretic hormone/other, who may benefit from treatment with tolvaptan, while excluding those who have acute or transient hyponatremia, have overt symptoms of hyponatremia requiring immediate intervention, or who are at increased risk for developing hyponatremic encephalopathy or osmotic demyelination.

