### 3.4.3 Exclusion Criteria

Subjects will be excluded if they meet any of the exclusion criteria in [Table 3.4.3-1](#).

Table 3.4.3-1 Exclusion Criteria	
1.	Has evidence of hypovolemia or intravascular volume depletion (eg, hypotension, clinical evidence of volume depletion, response to saline challenge); if the subject has systolic blood pressure or heart rate outside of the normal range for that age volume status should be specifically clinically assessed to rule out volume depletion.
2.	Has serum sodium $<$ 120 mEq/L (mmol/L), with or without associated neurologic impairment (ie, symptoms such as apathy, confusion, or seizures)
3.	Current use or expected use during the trial of a potent CYP3A4 inhibitor in subjects weighing $<$ 12 kg or a moderate CYP3A4 inhibitor in subjects weighing $<$ 6 kg
4.	Lacks free access to water (inability to respond to thirst) or without ICU-level fluid monitoring and management
5.	Has a history or current diagnosis of nephrotic syndrome
6.	Has transient hyponatremia likely to resolve (eg, head trauma or post-operative state)
7.	Has hyperkalemia defined as serum potassium above the ULN for the appropriate pediatric age range

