**Table 3.4.3-1      Exclusion Criteria**

Table 3.4.3-1 Exclusion Criteria	
8.	Has eGFR < 30 mL/min/1.73 m  calculated by the following equation: eGFR (mL/min/1.73 m  ) = 0.413 × height (cm)/serum creatinine (mg/dL)
9.	Has AKI defined as: 
 
• Increase in serum creatinine by ≥ 0.3 mg/dL (≥ 26.5 µmol/L) within 48 hours; or
 
• Increase in serum creatinine to ≥ 1.5 times baseline, which is known or presumed to have occurred within the prior 7 days; or
 
• Urine volume < 0.5 mL/kg/h for 6 hours
 

10.	Has severe or acute neurological symptoms requiring other intervention (eg, hyperemesis, obtundation, seizures)
11.	Has had treatment for hyponatremia with: 
 
• Hypertonic saline (including normal saline challenge) within 8 hours of qualifying serum sodium assessments;
 
• Urea, lithium, demeclocycline, conivaptan, or tolvaptan within 4 days of qualifying serum sodium assessments;
 
• Other treatment for the purpose of increasing serum sodium concurrent with dosing of trial medication
 

12.	Has anuria or urinary outflow obstruction, unless the subject is, or can be, catheterized during the trial
13.	Has a history of drug or medication abuse within 3 months prior to Screening or current alcohol abuse
14.	Has a history of hypersensitivity and/or idiosyncratic reaction to benzazepine or benzazepine derivatives (such as benazepril)
15.	Has psychogenic polydipsia (subjects with other psychiatric illness may be included per medical monitor approval)
16.	Has uncontrolled diabetes mellitus, defined as fasting glucose > 300 mg/dL (16.7 mEq/L [mmol/L])
17.	Has screening liver function values > 3 × ULN
18.	Subjects who have cirrhosis and meet any of the following conditions: a major GI bleed within the past 6 months, evidence of active bleeding (eg, epistaxis, petechiae/purpura, hematuria, or hematochezia), platelet count < 50,000/µL, or use of concomitant medications known to increase bleeding risk
19.	Has hyponatremia due to the result of any medication that can safely be withdrawn (eg, thiazide diuretics)
20.	Has hyponatremia (eg, hyponatremia in the setting of adrenal insufficiency, untreated hypothyroidism, or hypotonic fluid administration) that is most appropriately corrected by alternative therapies
21.	Is currently pregnant or breastfeeding

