22.	Has any medical condition that, in the opinion of the investigator, could interfere with evaluation of the trial objectives or safety of the subjects.
23.	Is deemed unsuitable for trial participation in the opinion of the investigator
24.	Participation in another investigational drug trial within the past 30 days, without prior approval from the sponsor medical monitor
25.	Subjects who weigh < 3 kg
26.	Unable to swallow tablets if the suspension formulation is unavailable
27.	Subjects who require the suspension formulation and have Hereditary Fructose Intolerance

eGFR = estimated glomerular filtration rate; ICU = intensive care unit.

Use of the suspension formulation is at the discretion of the local regulatory authorities and IRB/IECs.

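### Table 3.4.3-1 does not fully carry over the mandatory demyelination bar in Protocol Section 3.3: the sodium limit differs at exactly 120 mEq/L, and hypokalemia, hypoxemia, severe burns and severe malnutrition have no row

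*Protocol*

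**What the plan says.** The part of Protocol Section 3.3 on hyponatremia etiology uses two strengths of wording. For encephalopathy it is discretionary: "subjects with known risk factors for developing hyponatremic encephalopathy may be ineligible for tolvaptan treatment". For demyelination it is mandatory: "those subjects who are at risk of developing cerebral demyelination will be ineligible for tolvaptan treatment, including subjects who have severe hyponatremia", with the limit given as 120 mEq/L or below. The mandatory list then continues: "hypernatremia, hypoxemia, severe liver disease, alcoholism, severe burns, severe malnutrition, hypokalemia, diabetes, or renal failure".

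The Subject Population entry of the synopsis says the entry criteria are designed to keep out, among others, children "or who are at increased risk for developing hyponatremic encephalopathy or osmotic demyelination". The table is therefore meant to carry this bar.

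In Table 3.4.3-1, criterion 2 reads "Has serum sodium $<$ 120 mEq/L (mmol/L), with or without associated neurologic impairment", and the synopsis uses the same limit. The only row on serum potassium is criterion 7: "Has hyperkalemia defined as serum potassium above the ULN for the appropriate pediatric age range". For diabetes, criterion 16 reads "Has uncontrolled diabetes mellitus, defined as fasting glucose > 300 mg/dL". Criterion 22 is a general clause: "Has any medical condition that, in the opinion of the investigator, could interfere with evaluation of the trial objectives or safety of the subjects". Criterion 23 likewise leaves suitability to the investigator's opinion.

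**The concern.** Sites confirm eligibility against the inclusion and exclusion criteria at screening and again before the first dose (Table 3.7-1 footnote b; Section 3.7.1.2.1). A child with sodium of exactly 120, or with low potassium, passes every measurable row of that list although Section 3.3 bars the child.

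The stake is safety. Section 5.3.1.1 says that overly rapid correction may lead to osmotic demyelination, with severe brain damage or death. Dose holding, extra sodium samples and neurological examinations reduce the risk once dosing has begun, but they do not decide who is dosed.

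There is also a record-keeping side. Section 3.13 treats enrollment against the eligibility criteria as a significant deviation, and SAP Section 5.1.6 summarizes entry-criteria deviations. With two versions of the list, it is unclear whether such a child would be recorded as one.

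**Working it through.** No sample size, power or alpha figure is involved. The check sets the ten conditions named in Section 3.3 against the 27 rows of Table 3.4.3-1.

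| Section 3.3 | Nearest table row | Match |
|---|---|---|
| Sodium ≤ 120 mEq/L | 2: sodium < 120 | Differs at exactly 120 |
| Hypokalemia | None (7 is hyperkalemia) | No row |
| Hypoxemia | None | No row |
| Severe burns | None | No row |
| Severe malnutrition | None | No row |
| Diabetes (any) | 16: uncontrolled, fasting glucose > 300 mg/dL | Partial |
| Severe liver disease | 17: liver values > 3 × ULN; 18: cirrhosis with bleeding-related conditions | Partial |
| Renal failure | 8: eGFR < 30; 9: acute kidney injury; 12: anuria | Measurable limits present |
| Alcoholism | 13: current alcohol abuse | Broadly covered |
| Hypernatremia | Inclusion 3 requires sodium < 130 | Cannot arise |

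**Sodium.** Entry requires sodium below 130. Assuming results are reported in whole mEq/L, the table admits 120 to 129, which is 129 − 120 + 1 = 10 values. Section 3.3 admits 121 to 129, which is 129 − 121 + 1 = 9 values. They differ at 10 − 9 = 1 value, namely 120. This counts reportable values and is not a share of children.

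**Potassium.** Serum chemistry, which includes potassium as a priority test (Table 3.7.4.2.3-1), is scheduled at screening and then only at 72 hours after the last dose or at early termination (Table 3.7-1; Sections 3.7.1.1 and 3.7.1.4.1). The screening value is therefore the one scheduled trial measurement before dosing, and no row acts on a low result.

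**Is the text meant to bind?** Three things say yes:
- Section 3.3 separates mandatory from discretionary ineligibility within the same passage.
- The synopsis gives exclusion of demyelination risk as a purpose of the entry criteria.
- Other bars stated in the text do reach the table: hereditary fructose intolerance (criterion 27), weight below 3 kg (25) and the CYP3A4 inhibitor limits (3).

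**Overlap within Section 3.3.** Hypoxia is on the discretionary encephalopathy list and hypoxemia is on the mandatory demyelination list. A site reading both could reach either answer.

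**The case against.** The strongest reply is that the protocol already bars these children. Section 3.3 is current, mandatory text, and a site that doses such a child has breached it. Screening is also more than a checklist. Footnote h of Table 3.7-1 requires a clinical status assessment before the first dose, covering trial and non-trial laboratory results. Section 5.1 requires the investigator to review every laboratory result and sign and date the report. Criteria 22 and 23 then allow exclusion. This stands, and it limits the point to incomplete carry-over. It does not remove it, because the review is compulsory but its conclusion is left to judgment, whereas Section 3.3 leaves none.

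A second reply is that the sodium discrepancy could equally be removed by relaxing Section 3.3 to below 120. That would be consistent, but it loosens a stated safety bar, and the documents offer no reason to do so. Moving the table to 120 or below excludes nobody whom Section 3.3 does not already bar.

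A third reply is that Section 3.3 gives no potassium threshold, so any cutoff is a choice. That is right, and the choice belongs to the sponsor. It matters in practice because steady diuretic doses are acceptable in heart failure (Section 3.3.1.2) and recruitment was expected to be difficult (Section 2.1).

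A reader might infer that the protocol permits dosing of these children, or that two opposite rules are in force. The documents do not support either reading: the table is silent or narrower, and nothing in it overrides Section 3.3. Nor do they show that any such child was dosed. The listing of hypokalaemia among events in more than 5% of adult tolvaptan subjects (Section 1.3) is an on-treatment adult figure and gives no baseline rate in children.

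**Conclusion.** The point holds as an incomplete carry-over of a mandatory safety bar into the checked criteria. One limit differs (sodium, at exactly 120) and four named conditions have no row. Diabetes and severe liver disease are covered only in part. Which direction is right for those two cannot be settled from the documents, so they should not be counted either as clear gaps or as full matches.

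The sodium gap is one reportable value, on the assumption of whole-number results. The documents give no prevalence for any of the conditions. SAP Section 5.1 records extremely low enrollment and early termination, so the number of children affected is unknown and may be small. No endpoint, analysis, power or alpha figure changes. The correction is still worth making because it concerns who may be dosed and needs no new test.

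**What to change.** 1. Change criterion 2 and the matching synopsis entry to *serum sodium ≤ 120 mEq/L (mmol/L)*, so that all three places state one limit.
2. Add one row to Table 3.4.3-1 excluding subjects with hypokalemia, hypoxemia, severe burns or severe malnutrition as listed in Section 3.3. Judge these on the screening chemistry already drawn and on history or routine care.
3. Have the sponsor set the potassium cutoff. A value below the age-specific lower limit of normal would mirror criterion 7. State that a child may be rescreened after correction if undosed, as Section 3.9 already allows.
4. In Section 3.3, take hypoxia off the discretionary list or align it with hypoxemia.
5. Ask the sponsor's clinicians to decide how the diabetes and severe liver disease wording should be reconciled with criteria 16 to 18. Section 3.3.1.2 shows that children with hepatocellular disease are part of the intended population, so a blanket change in either direction needs clinical grounds.

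The cost is one clarifying amendment with no added procedure. The downside is that a child at exactly 120, or with low potassium, is delayed or excluded, which Section 3.3 already requires.

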### **3.2.3 Dosing Guidelines**

Subjects will be administered tolvaptan on a formulation, age- and weight-based scale.

**Table 3.2.3-1** outlines starting tolvaptan doses and adjustments when tolvaptan is administered concurrently with potent or moderate CYP3A inhibitors. Tolvaptan doses will be reduced 75% and 50% if a potent or moderate inhibitor, respectively, is being concurrently administered. As the smallest volume of suspension that can be administered is 0.3 mL (0.3 mg), subjects weighing < 3 kg, < 6 kg and taking a moderate or a potent CYP3A4 inhibitor, or weighing < 12 kg and taking a potent CYP3A4 inhibitor may not be enrolled. Suspension should be administered with the syringes provided.

Table 3.2.3-1 Starting Tolvaptan Doses With or Without Potent or Moderate CYP3A Inhibitors				
Age/Weight	Can subject swallow a tablet?	Starting Dose: No CYP Inhibitor	Starting Dose: Moderate CYP Inhibitor	Starting Dose: Potent CYP Inhibitor
≥ 4 wk (or ≥ 44 wk adjusted gestational age) to < 2 y AND ≥ 3 kg to < 6 kg c	N/A	0.1 mg/kg suspension a,b	Not eligible for treatment	Not eligible for treatment
≥ 4 wk (or ≥ 44 wk adjusted gestational age) to < 2 y AND ≥ 6 to < 12 kg c	N/A	0.1 mg/kg suspension a,b	0.05 mg/kg suspension	Not eligible for treatment
≥ 2 y to ≤ 6 y AND ≤ 30 kg c	N/A	0.15 mg/kg suspension	0.08 mg/kg suspension	0.04 mg/kg suspension
> 6 y AND ≤ 30 kg	No	0.15 mg/kg suspension	0.08 mg/kg suspension	0.04 mg/kg suspension
> 6 y AND 20 to 50 kg	Yes	7.5 mg tablet	3.75 mg tablet	1.90 mL suspension
> 6 y AND > 50 kg	Yes	15 mg tablet	7.5 mg tablet	3.75 mg tablet

a The smallest volume of suspension that may be administered is 0.3 mL (0.3 mg), therefore dose reductions cannot be accommodated for children < 6 kg taking moderate inhibitors and for children < 12 kg taking potent inhibitors.

b Tolvaptan suspension is provided in a concentration of 1 mg/mL.

c Suspension required (pediatric subjects ≤ 6 years of age and ≤ 30 kg body weight).

Titration of tolvaptan doses can occur once daily and will be based on serum sodium levels assessed at > 20 hours following initiation of therapy and each subsequent dose; titration may not occur within 24 (± 4) hours of the previous dose. Up-titration is limited to no more than twice the previous dose.

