- Subjects ≥ 4 weeks (or ≥ 44 weeks adjusted gestational age) to < 2 years of age and weighing ≥ 3 kg to < 6 kg will receive 0.1 mg/kg of the suspension on Day 1 with possible up-titration to 0.2 mg/kg and 0.4 mg/kg doses.
- Subjects ≥ 4 weeks (or ≥ 44 weeks adjusted gestational age) to < 2 years of age and weighing ≥ 6 kg to < 12 kg will receive 0.1 mg/kg of the suspension on Day 1 with possible up-titration to 0.2 mg/kg and 0.4 mg/kg doses.

- Subjects  $\geq 2$  to  $\leq 6$  years of age, weighing  $\leq 30$  kg will receive a 0.15 mg/kg dose of the suspension on Day 1 with possible up-titration to 0.3 mg/kg and 0.6 mg/kg doses.
- Subjects  $> 6$  years of age, weighing  $\leq 30$  kg and who cannot safely swallow a tablet, will receive a 0.15 mg/kg dose of the suspension on Day 1 with possible up-titration to 0.3 mg/kg and 0.6 mg/kg doses.
- Subjects  $> 6$  years of age and weighing 20 to 50 kg, inclusive, will receive a 7.5 mg tablet on Day 1 with possible up-titration to 15-mg and 30-mg doses.
- Subjects  $> 6$  years of age and weighing  $> 50$  kg, will receive a 15 mg tablet on Day 1 with possible up-titration to 30-mg and 60-mg doses.

[figure not shown]
Following their initial tolvaptan dose in the trial, subjects will continue dosing according to the titration scheme (see [Section 3.2.4](#)), targeting a final serum sodium concentration between 135 and 140 mEq/L (mmol/L). Titration guidelines are designed to achieve a change in serum sodium concentration of at least 4 to 8 mEq/L (mmol/L)/24 hours but not [REDACTED].

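### The routine pre-entry history for hereditary fructose intolerance starts only above 2 years, although every dosed child under 2, and a child of exactly 2 at up to 30 kg, can receive only the sorbitol suspension

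*Protocol*

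**What the plan says.** Protocol Section 3.3, under Hyponatremia Etiology in Children and Adolescents, explains that the suspension contains sorbitol and concludes: "Therefore, children who have HFI should not take the tolvaptan suspension formulation". On when the disorder comes to light it says: "Hereditary fructose intolerance is typically diagnosed in young children upon the introduction of solid foods containing fructose, sucrose and/or sorbitol", and adds: "It is not commonly diagnosed in children who are fed exclusively on breast milk". For a child already under suspicion, with no age limit, it asks for more: "If HFI is suspected, a thorough history that emphasizes nutritional complaints", including when fruit and vegetables were introduced, plus confirmatory laboratory work. The routine requirement closes the passage: "For children aged > 2 years, a detailed history with regard to HFI symptoms has to be taken prior to trial entry".

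Section 3.2.3 assigns the formulation. The lightest group under 2 is typical: from 4 weeks "to < 2 years of age and weighing ≥ 3 kg to < 6 kg will receive 0.1 mg/kg of the suspension". The 6 to < 12 kg group under 2 also gets suspension. Footnote c of Table 3.2.3-1, attached to these rows and to the row from 2 to 6 years, reads: "Suspension required (pediatric subjects ≤ 6 years of age and ≤ 30 kg body weight".

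Exclusion 27 in Table 3.4.3-1 bars "Subjects who require the suspension formulation and have Hereditary Fructose Intolerance". It has no age limit and names no means of detection.

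**The concern.** The history exists to make exclusion 27 workable, yet its age limit does not follow exposure to the suspension. Children under 2 who have a dose row receive sorbitol without exception, and they are the ones for whom the detailed history is not required. Some older children who take only tablets must give it.

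At stake are the safety of a child with unrecognized HFI and the reading of the safety data. Section 3.3 lists vomiting, lethargy, raised transaminases, raised bilirubin and clotting disturbance among the features of HFI. Vomiting and lethargy are also listed there as symptoms of hyponatremic encephalopathy, and raised transaminases with raised bilirubin trigger reporting as potential drug-induced liver injury under Section 5.4. A missed case could be attributed to tolvaptan or to the underlying condition.

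**Working it through.** **The protocol's own sorbitol figure.** Section 1.3 gives 8 g of sorbitol in a 15 mg dose. At 1 mg/mL that is 8 / 15 = 0.533 g/mL. A 30 kg child at 0.6 mg/kg takes 30 × 0.6 / 1 = 18 mL, and 18 × 0.533 = 9.6 g. This matches the amount in Sections 1.3 and 2.1.1.

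**Load below 2 years.** Daily sorbitol = weight × dose (mg/kg) / 1 mg/mL × 0.533 g/mL, for the doses listed without a CYP3A inhibitor.
- Lowest: 3 kg × 0.1 = 0.3 mL, giving 0.16 g.
- Highest: 11.9 kg × 0.4 = 4.76 mL, giving 2.54 g.

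The top dose needs two doublings, and Section 3.2.4 allows up-titration only on Day 2 or 2a, so it is first reachable on Day 2a. Treatment lasts at most 5 days.

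**Formulation against the history requirement** (Table 3.2.3-1 against Section 3.3):

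| Group | Formulation | Routine HFI history required |
|---|---|---|
| < 2 y, 3 to < 6 kg | suspension | no |
| < 2 y, 6 to < 12 kg | suspension | no |
| exactly 2 y, ≤ 30 kg | suspension | no |
| > 2 to 6 y, ≤ 30 kg | suspension | yes |
| > 6 y, ≤ 30 kg, cannot swallow tablets | suspension | yes |
| > 6 y, 20 to 50 kg, swallows tablets, no or moderate inhibitor | tablet | yes |
| > 6 y, 20 to 50 kg, swallows tablets, potent inhibitor | suspension (1.90 mL) | yes |
| > 6 y, > 50 kg | tablet | yes |

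A child under 2 weighing 12 kg or more has no dose row, so the statement covers every child under 2 who has an assigned dose. The gap at exactly 2 years comes from the history starting above 2 while the dosing row starts at 2.

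**Does another step supply the history?** Section 3.7.1.1 asks for medical problems that bear on the current hospital stay and for the hyponatremia history. Neither that list nor Table 3.7-1 contains an HFI or feeding item, so even the history required above 2 years has no entry of its own in the schedule.

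**The case against.** The strongest reply is that children under 2 are not left without a check. Exclusion 27 applies at every age, and the criteria are reviewed at screening and confirmed before the first dose on Day 1. The work-up of a suspected case has no age limit. All subjects have chemistry, coagulation and urinalysis at screening, liver values above 3 × ULN exclude, and the cause of hepatocellular disease must be documented. This stands, so a reader who inferred that nobody need consider HFI in an infant would be wrong. What remains is narrower: these steps work only if HFI is known or suspected, or if an abnormality is already present. The routine history is the step that would raise suspicion.

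A second reply is that a symptom history tells little in an infant not yet exposed to fructose. That may be why the limit exists, but the protocol does not say so, and it would not explain omitting weaned children under 2.

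Three stronger readings are not supported.
- A reader might infer that the protocol itself places the onset of HFI below 2 years. It names a feeding stage and gives no age. That solids usually start before 2 is an inference, though a natural one.
- A reader might compare the sorbitol loads with the 200 mg daily figure in Section 1.3 and treat the ratio as a measure of HFI risk. That figure counts sorbitol used as a food ingredient and is quoted in a discussion of osmotic diarrhea. It is not total fructose-yielding intake, and the lowest load above, 0.16 g, is below it.
- A reader might infer that children in the tablet weight bands never receive sorbitol. Those over 6 years and 20 to 50 kg on a potent CYP3A inhibitor do.

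**Conclusion.** The point holds as a mismatch between an age limit and the exclusion it serves. Both dose rows below 2 years, and the row that takes in exactly 2 years, are suspension only, and none of these children falls under the required history. Daily sorbitol in the groups under 2 runs from 0.16 to about 2.5 g without an inhibitor.

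No case count can be given. The documents state neither how common HFI is nor how many children under 2 are expected; the quota of at least 25% under 6 years does not answer that. The practical weight of the gap rests on the assumption that some enrolled children under 2 are already weaned. It arises only where the suspension is available, since exclusion 26 keeps out those who cannot swallow tablets elsewhere. SAP Section 5.1 records very low enrollment and early termination, so the benefit now lies mainly in any reuse of this text. It is a modest safety gap that is cheap to close.

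**What to change.** Reconcile Section 3.3, Section 3.2.3 with Table 3.2.3-1, and exclusion 27, so that the pre-entry HFI history follows assignment to the suspension instead of the limit above 2 years, or else state the reason for that limit. Following assignment would also cover the child of exactly 2 and would tie the requirement for older children on a potent inhibitor to their actual exposure. Carry the resulting step into Section 3.7.1.1 and Table 3.7-1 so that sites see it in the schedule they work from. The clinical content of the history is for the sponsor to decide.

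The cost is a revised sentence, a screening step, a schedule row and a few more questions, with no added test or visit. The drawback is that the answers are less informative before weaning.
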